### 6.5.3 Covariates

A range of demographics will be assessed for each patient at cohort entry, including the following:

- Age;
- Sex;
- Race/ethnicity.

A set of comorbidities will be assessed in the 180 days before cohort entry, including the following:

- Acute myocardial infarction;
- Stroke;
- Dyslipidemia;
- Type 2 diabetes mellitus;
- Transient ischemic attack;
- Hypertension;
- Heart failure;
- Unstable angina;
- Peripheral vascular disease;
- Coronary heart disease;
- Cerebrovascular disease;
- Chronic kidney disease;

- Sleep apnea;
- Mood disorders.

A set of concomitant medications will be assessed in the 180 days before cohort entry, including the following:

- Medications that affect cardiovascular outcomes, including:
  - Antihypertensives;
  - Statins;
  - Anticoagulants;
  - Antiplatelets;
  - Antihyperglycemics.
- Other medications listed in the CONTRAVERE® Prescribing Information Drug Interactions, including:
  - Selective serotonin reuptake inhibitors;
  - Tricyclic antidepressants;
  - Antipsychotics;
  - Beta-blockers;
  - Type 1C antiarrhythmics (e.g., propafenone and flecainide);
  - Digoxin;
  - Antiplatelets.

A set of relevant laboratory test results and biometric values will be assessed during the 180 days before cohort entry, including the following:

- BMI;
- Blood glucose or HbA1c;
- Liver function;
- Dyslipidemias;
- Resting heart rate;
- Respiratory rate;
- Systolic blood pressure;
- Diastolic blood pressure;
- Glomerular filtration rate/serum creatinine.

Where multiple values are available, the most recent will be selected. Where no value is present, multiple imputation procedures will be used to generate a value under the assumption that the values are missing at random.

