### 6.2 Settings

The cohorts for all study objectives will be drawn from a large EHR data source, representing a geographically diverse patient population. The data will include diagnoses, procedures, medications (prescribed and administered), clinical measures (biometric and laboratory values), and observations derived from clinical notes. A subset of the population will have linked, adjudicated claims data available to support sensitivity analyses.

EHR data, generated from routine clinical care offer timely clinical information not typically available in claims databases, including information on patient attributes, observations from physicians' notes, patient symptoms and history, diagnostic information, and planned and actual treatments, and prescription medicines not covered by health plans (e.g., CONTRAVE®). Notably, EHR data include measures of BMI for descriptive analysis and evaluation as a potential confounder and effect modifier. These EHR data will be linked to proprietary information from First Databank to identify medications of interest accurately, including NB.

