## 9.4 PS Matching Weights

PS matching weights will be used to control for confounding between treatment groups. A logistic regression model will be used to estimate the predicted probability of treatment with NB versus treatment with lorcaserin, conditional on pre-specified covariates. Each patient's PS, or predicted probability from the model, will be the probability that the patient received NB. The complement of each patient's PS (i.e., 1-PS) will be the probability that the patient received lorcaserin. Each patient will be assigned a matching weight, which is a function of their PS and the treatment received. The numerator of the matching weight is the smaller of the PS or the complement of the PS (1-PS). The denominator is the PS if the patient received NB, and it is 1-PS if the patient received lorcaserin. For example, a patient with a PS value of 0.6 (1-PS = 0.4) who received NB would have a matching weight of 0.4/0.6 or 0.667. These weights will be used in regression models to account for confounding.

Similar methods will be used to generate propensity score weights within the CAMELLIA-TIMI 61 comparability cohort. Covariates will include demographics, calendar time of treatment initiation, comorbidities, medications, cardiovascular procedures, and indicators of health care utilization as proxy for overall disease state, care intensity, and surveillance.

Matching weights are the weighting analog of 1:1 PS matching, but include the entire eligible patient population, are more statistically efficient than matching, and produce better balance on covariates. Thus, matching weights standardize the distribution of patient characteristics to the area of common support (or empirical equipoise) in which patients could have reasonably received either treatment.

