### 10.2 Unmeasured Patient Risk Factors

In this study, robust PS adjustment relies on accurate measurement of risk factors for MACE. As such, the lack of important risk factors can introduce unmeasured confounding, where these risk factors remain imbalanced between groups after PS adjustment. The use of an active comparator will mitigate some unmeasured confounding, because it shares the same indication as NB. Self-controlled designs are not subject to measured or unmeasured confounding by factors that do not vary over the observation window. Therefore, the case-crossover study will help inform the extent to which residual confounding may affect the cohort analysis.

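### The plan does not commit to measuring or balancing smoking, a major risk factor for MACE, in the NB-versus-lorcaserin comparison

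*Combined protocol and SAP*

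**What the plan says.** Section 6.5.3 gives four groups of covariates, each with an itemised list:

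- Demographics: "A range of demographics will be assessed for each patient at cohort entry, including the following". The items are age, sex and race/ethnicity.
- Comorbidities: "A set of comorbidities will be assessed in the 180 days before cohort entry, including the following". There are 14 items, from acute myocardial infarction to mood disorders.
- Medications: "A set of concomitant medications will be assessed in the 180 days before cohort entry, including the following". The items are cardiovascular classes and drugs from the label's interaction section.
- Laboratory and biometric values: "A set of relevant laboratory test results and biometric values will be assessed during the 180 days before cohort entry, including the following". The items run from BMI to renal function.

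Section 9.4 estimates the propensity score (PS) for NB versus lorcaserin "conditional on pre-specified covariates". For the comparability cohort it adds: "Covariates will include demographics, calendar time of treatment initiation, comorbidities, medications, cardiovascular procedures, and indicators of health care utilization". Section 9.5.3 adjusts the weighted Poisson models for the covariates in the PS model. Section 9.1 judges balance by standardized differences between the weighted groups.

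Section 10.2 says that "robust PS adjustment relies on accurate measurement of risk factors for MACE". It accepts in general terms that a missing risk factor can confound the comparison, and it offers the active comparator and the case-crossover study as mitigation. Section 6.2 says that the source includes "observations derived from clinical notes".

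**The concern.** Smoking is a major risk factor for myocardial infarction and stroke, two of the three components of the primary endpoint. (This is general clinical knowledge; the documents do not discuss it.) The words smoking, tobacco and nicotine occur nowhere in the readable text, whether as covariate, criterion, subgroup or limitation.

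An analyst who follows the named lists would leave smoking out of the weights, the outcome model and the balance table. If smoking differs between arms, the primary IRR and IRD would carry that difference. The balance table could still look satisfactory, because it reports only the variables given to it. More smokers on NB would push the result towards apparent harm, and fewer would hide real harm. Section 13 sends the results to FDA as cardiovascular safety evidence, so an unexplained omission of smoking invites an obvious challenge.

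**Working it through.** **Does any part of the plan bring smoking in?**

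1. Section 6.5.3: none of the four lists contains tobacco use. The medication list has no smoking-cessation class that could act as a proxy.
2. Section 9.4: the main PS model uses pre-specified covariates. The comparability list adds calendar time, cardiovascular procedures and utilization, but no lifestyle factor.
3. Section 9.5.3: the outcome model uses the PS covariates, so it adds nothing.
4. Section 9.1: balance is assessed on the plan's covariates, so an unlisted variable has no assured place in the table.
5. Section 10.2: smoking is not disclosed as unmeasured.

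**How large could the effect be?** The plan gives no figure to reproduce. For a binary unmeasured confounder, the factor by which the IRR is multiplied is

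B = [1 + p_NB(RR − 1)] / [1 + p_L(RR − 1)],

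where p_NB and p_L are the smoking prevalences in the weighted NB and lorcaserin groups and RR is the smoking-MACE rate ratio. None of these inputs is in the documents; all are assumed.

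| p_NB | p_L | RR 1.5 | RR 2 | RR 3 |
|---|---|---|---|---|
| 10% | 10% | 1.00 | 1.00 | 1.00 |
| 15% | 10% | 1.075/1.05 = 1.02 | 1.15/1.10 = 1.05 | 1.30/1.20 = 1.08 |
| 20% | 10% | 1.10/1.05 = 1.05 | 1.20/1.10 = 1.09 | 1.40/1.20 = 1.17 |
| 10% | 20% | 1.05/1.10 = 0.95 | 1.10/1.20 = 0.92 | 1.20/1.40 = 0.86 |

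**On the absolute scale.** Take the planning rate of 2 per 1,000 person-years (section 8.2) as the observed lorcaserin rate and assume no true effect. The spurious IRD at the extremes is then 2 × (1.40/1.20 − 1) = +0.33 and 2 × (1.20/1.40 − 1) = −0.29 per 1,000 person-years.

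**Masking.** At the lower extreme, a true IRR of 1.17 (1.40/1.20) would be observed as 1.40/1.20 × 1.20/1.40 = 1.00.

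**The case against.** The best defence is that the lists are open. Each is introduced as a set of inclusions, and the Abstract names observations as a further source of covariates without itemising them. Figure 1 is not available in the text reviewed. A reader might infer from the omission that smoking will certainly go uncontrolled. The documents do not support that; they show only that the plan makes no commitment. The point survives, because a PS model built on pre-specified covariates needs its main confounders named before results are seen.

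A reader might also infer that smokers were steered towards NB because it contains bupropion, so that the bias runs towards harm. The documents do not support this either. Section 2 describes bupropion only as an antidepressant, and nothing in the plan shows that smoking differs between the arms or in which direction.

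Section 10.2's mitigations have some force. Lorcaserin shares NB's indication, which the plan says removes some unmeasured confounding; it does not claim to remove all of it. The case-crossover study cancels smoking that is stable across its windows and is meant to inform the extent of residual confounding. However, it concerns NB only and cannot correct the NB-versus-lorcaserin IRR or IRD.

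Two further objections stand. The listed vascular diagnoses, blood pressure and cardiovascular drugs may correlate with smoking, and balancing them could shrink the residual difference. Also, no section confirms that the source holds a smoking field; sections 6.2 and 7.1 only make it plausible, through patient attributes, note-derived observations, medical history and problem lists.

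**Conclusion.** The concern holds as a gap in commitment. Smoking is absent from the covariates itemised in section 6.5.3 and from the comparability list in section 9.4, and section 10.2 does not declare it unmeasured. This falls short of the plan's own condition for valid PS adjustment in its primary comparison.

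Whether the estimate would be biased, and which way, cannot be determined from the documents. The illustrative factors of 0.86 to 0.95 and 1.05 to 1.17 rest on an assumed twofold prevalence gap, an assumed rate ratio of 1.5 to 3 that is the same in both arms, and no reduction through correlated covariates. Bias of that size would not by itself produce the relative risk of 2.0 used in section 8.2, but it could create or hide a modest difference. The textual omission is certain; everything about magnitude is conditional. The plan should be changed, but the study is not invalid as it stands.

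**What to change.** Add baseline tobacco status (current, former, never) to section 6.5.3. Take it from the most recent record on or before cohort entry, using EHR history, clinical-note observations and diagnosis codes. Include it in the main and comparability PS models, in the imputation model of section 9.2 and in the standardized-difference table of section 9.1.

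Check completeness by arm before outcomes are analysed. If capture proves inadequate, name smoking in section 10.2 as an unmeasured risk factor and report a quantitative bias analysis over stated prevalences and rate ratios in both directions, as tabulated above.

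The study is retrospective, so no new patient contact is needed. The costs are some extraction work, particularly from notes, and incomplete recording that must go through the planned multiple imputation and so rests on its missing-at-random assumption.

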## 7 DATA SOURCES

### 7.1 Arcadia Data Research

The study will use EHR data and linked claims data from Arcadia, which has assembled one of the largest EHR datasets available to life science organizations, currently covering approximately 75 million individuals in the U.S. Arcadia partners with health systems and payers to create a centralized, physically integrated EHR system that has nationwide coverage and integrates clinical data from multiple electronic medical records within and across health systems via their Master Patient Index, a proprietary person-matching technology that identifies distinct patients across disparate data sources. The typical research extract includes patient demographics, encounters, appointments, provider data, charges, assessments, immunizations, health maintenance and medical history, orders/results, vitals, insurance, prescriptions and active medications, problem lists, and allergy information.

Arcadia's EHR data are sourced from large integrated delivery networks, academic medical centers, ambulatory, primary care, core hospitals, and other providers. Arcadia's de-identified dataset for research includes a mix of populations representing individuals with commercial insurance, along with Medicare and Medicaid coverage. Adjudicated claims data from multiple payers are available for approximately 46% of the EHR patients.

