### 6.3 Inclusion Criteria

For the main objective (1.0, 1.1), patients are eligible if they meet the following inclusion criteria:

- Have at least one prescription for NB between September 2014 and February 2020, including concurrent prescriptions (within 15 days) for naltrexone and bupropion; or have at least one prescription for lorcaserin;
- Have at least 180 days of data available prior to cohort entry with no evidence of prescriptions or dispensings of NB or lorcaserin;
- Have at least one BMI value available in the 180 days prior to cohort entry, inclusive of the index date;
- Have documentation of at least one outpatient medical visit 180 or more days prior to cohort entry, and at least one healthcare interaction in the 180 days prior to cohort entry;

- Are at least 18 years of age on the cohort entry date.

Of note, having at least one BMI value is the only inclusion criterion that is potentially missing within the EHR. Documentation of at least one outpatient medical visit more than 180 days prior to cohort entry, and at least one healthcare interaction in the 180 days prior to cohort entry is required. This criteria will facilitate the inclusion of individuals who appear to have sufficient engagement with an Arcadia-contributing health system and would have enough clinical data to meet the study objectives.

For the comparability study (2.0 and 2.1), inclusion criteria will be based on the CAMELLIA-TIMI 61 trial, insofar as the information is available in the data. Examples include:

- BMI  $\geq 27 \text{ kg/m}^2$ ;
- Age  $\geq 40$  years with history of documented myocardial infarction (MI) or ischemic stroke  $> 1$  month prior to baseline, peripheral artery disease, revascularization or significant unrevascularized coronary arterial stenosis;
- Women age  $\geq 55$  years or men age  $\geq 50$  years who have type 2 diabetes mellitus without established cardiovascular disease but at least one cardiovascular risk factor (hypertension, dyslipidemia, calculated creatinine clearance  $\geq 30$  to  $\leq 60 \text{ mL/min}$ , or urinary albumin-to-creatinine ratio  $\geq 30 \text{ } \mu\text{g/mg}$ ).

The full list of inclusion criteria are included in the CAMELLIA-TIMI 61 publication and protocol.

Where variables are not available in the EHR or claims data, we will search for suitable proxies based on the literature and the recommendations of a U.S.-licensed physician consultant.

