**Figure 2. Case-crossover study design**

### 6.5.2 Outcomes and follow-up

The primary study endpoint is MACE, defined as the composite of:

- Medically attended non-fatal acute myocardial infarction;
- Medically attended non-fatal stroke;
- Cardiovascular-related death.

The secondary endpoints are:

- Individual components of MACE, analyzed separately, as (1) medically attended non-fatal acute myocardial infarction; (2) medically attended non-fatal stroke; and (3) cardiovascular-related death.

In accordance with the CAMELLIA-TIMI 61 trial, the comparability study will examine safety endpoints for the secondary objectives (2.0 and 2.1).

The safety endpoint was defined as a composite of:

- Cardiovascular death;
- Myocardial infarction;
- Stroke.

For all study objectives, information on myocardial infarction and stroke will be obtained from the EHR data, while information on death will be obtained from Datavant. Datavant compiles mortality data from government sources, obituaries, newspapers, and claims data for more than 90% of the U.S. population. Cause of death will be ascertained from the subset of individuals whose records can be linked to death certificates; otherwise, diagnoses adjacent to death will be identified, as feasible, using information from the EHR (e.g., cardiovascular-related hospitalizations or emergency department visits immediately preceding date of death).

A U.S.-licensed physician consultant, blinded to exposure, will review the detailed chronological listing of individual-level EHR data (and claims, where relevant) of a randomly selected subset of apparent MACE cases to determine whether MACE occurred. The adjudication process will compare the operational definition of MACE in the EHR to the physician's professional judgement and the occurrence of MACE in the EHR and claims data. If the initial EHR-based definition of MACE does not meet a pre-specified threshold for concordance, then adjustments to the initial list of diagnoses and procedure codes will be made to improve the accuracy of the operational definition of MACE.

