Follow-up time will be calculated separately for each study endpoint. Patients will be followed starting the day after initial exposure until the first of the following censoring events: (1) the study endpoint of interest, (2) death (for those who do not have the endpoint of interest), or (3) end of available data for those who do not have the event of interest (i.e., censoring due to end of available EHR data). Person-time will be calculated by summing the days from cohort entry (day 0) to the date of the first relevant censoring event.

To test the robustness of assumptions about the date of censoring, analyses with differing censoring definitions will be performed, and estimates compared:

- To assess whether the censoring date needs to be adjusted, the physician consultant will review a random sample of patient health profiles to determine whether there is a clear indicator of censoring. Insofar as there appears to be a clear indicator of censoring, the physician will record this date (blinded to exposure), and this information will be used to

adjust the censoring date. Indeed, this information may be treated as an annotation for a machine learning model.

- To account for a patient still being on the insurance plan but not accessing the healthcare system, adjust the end of follow-up to be 6 months, 1 and 2 years following their last healthcare encounter in the EHR.
- To assess the reliability of our method for computing time until censoring in the EHR, compare follow-up times in the EHR to those observed in the claims enrollment files using a subset of those with EHR and claims data.
- To test robustness of the method for computing follow-up time in the EHR, compute the distribution of follow-up times based on enrollment spans within the subset of individuals with claims and EHR data and apply the median follow-up time within populations with particular health profiles.
- To implement a more specific definition of follow-up time, assume that a last healthcare encounter with a primary care provider, endocrinologist, or geriatric care provider in combination with no death information is the end of enrollment.

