### 9.5.3 Statistical Model for Cohort Analysis

For all primary study objectives, weighted Poisson models will be used to estimate IRDs and IRRs (and 95% CIs), adjusted for all covariates included in the PS model. Robust variance estimators will be used to account for the weighting. Analyses will be conducted amongst the overall NB cohort and also stratified by initiators of CONTRAVE® and those with overlapping, concomitant use of Naltrexone and Bupropion.

For the secondary objective of assessing the comparability of findings in a RWD cohort with the lorcaserin clinical trial, we will conduct a time-to event analysis in the propensity-score matched cohort. We will produce hazard ratios (HR) and 95% confidence intervals using a weighted Cox proportional-hazards model with the stratification factor as a covariate.

Additionally, informed by previous work in the RCT DUPLICATE Initiative, we will examine the following metrics in concert to assess the comparability in findings between the CAMELLIA-TIMI 61 trial and findings in the data:

- Regulatory agreement, which is the ability of the study using RWD to replicate the direction and magnitude of the RCT;

- Estimate agreement, defined as a HR from the replication study that was within the 95% CI for the RCT estimate;
- Standardized difference between the RCT and replication effect estimate, with a p-value < 0.05 considered statistically significant.

Conditional logistic regression models will be used to compare the odds of exposure to NB in the hazard window to the odds of exposure in the referent window (i.e., odds ratio) for the case cross-over design.

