## 10 LIMITATIONS OF THE DATA AND RESEARCH METHODS

### 10.1 Electronic Health Data

All EHR databases and healthcare registries have certain inherent limitations because the data are collected for clinical patient management, administration, and other non-research purposes. EHR data represent the intent of the prescriber through the written prescription for a medication; they do not indicate that a medication was filled, consumed, or taken as prescribed.

The EHR data will not include healthcare encounters or prescriptions from providers that do not contribute to the EHR aggregating entity (Arcadia). This can result in under-capture of some medication exposure. In addition, patients prescribed medications may not have them dispensed and may not consume them as prescribed even when they are dispensed. This can overestimate some patients' actual medication exposure.

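### MI and stroke are read from EHR contributors that need not hold hospital records; missed events are neither measured nor clearly adjusted for, so the IRD can shrink and unequal capture by drug would bias the IRR

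*Combined protocol and SAP*

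**What the plan says.** - **Outcome source.** Section 6.5.2: for every objective, "information on myocardial infarction and stroke will be obtained from the EHR data". Deaths come from an external death index. Cause of death comes from linked death certificates where they exist, otherwise from EHR diagnoses near death where feasible.
- **Contributors.** Section 7.1: "EHR data are sourced from large integrated delivery networks, academic medical centers, ambulatory, primary care, core hospitals, and other providers". The shares of each type are not given.
- **Eligibility.** Section 6.3 has two engagement rules. The rule on older history reads "Have documentation of at least one outpatient medical visit 180 or more days prior to cohort entry". The rule on recent contact, which does not specify the setting, asks for "at least one healthcare interaction in the 180 days prior to cohort entry".
- **Person-time.** Section 6.5.2: follow-up runs to the endpoint, death, or "end of available data for those who do not have the event of interest".
- **Adjustment.** Section 9.4 estimates the propensity score "conditional on pre-specified covariates". The list in section 6.5.3 has demographics, comorbidities, medications, laboratory values and biometrics. It has no contributor, contributor type or hospital-capture variable. Health care utilization as a proxy for surveillance is named in section 9.4, in the paragraph on the comparability cohort.
- **Estimands.** Section 9.5.3: "weighted Poisson models will be used to estimate IRDs and IRRs (and 95% CIs), adjusted for all covariates included in the PS model".
- **Stated limitation.** Section 10.1: "The EHR data will not include healthcare encounters or prescriptions from providers that do not contribute" to the aggregator. The consequence it draws is under-capture of medication exposure; endpoints are not mentioned.

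**The concern.** Acute MI and stroke are treated mainly in hospitals and emergency departments. A patient known to the database only through an office practice can satisfy every engagement rule and contribute follow-up to the end of the EHR data, although an admission to a non-contributing hospital would not be in the record as an encounter. Some person-time may therefore show little or no MI or stroke.

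Two results are at stake. The IRD is a planned primary estimate and falls in proportion to capture even when capture is the same for both drugs. The IRR is protected only if capture is the same. If NB and lorcaserin were prescribed in different kinds of contributing practice, balancing baseline cardiovascular risk would not balance the chance that an event is seen. In a safety study, lower capture among NB initiators would be falsely reassuring.

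**Working it through.** **1. Does a planned check measure missed events?**

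- Physician review (6.5.2) samples apparent MACE cases. It can find false positives and refine code lists, but cannot recover an event that never reached the record.
- The specified claims comparisons concern prescriptions against fills (6.5.1) and follow-up time (6.5.2). Neither estimates EHR sensitivity for MI or stroke.
- The alternative censoring rules (6.5.2) change when follow-up ends, not whether hospital events are visible during it.
- The person-matching index (7.1) joins records among contributing sources only.

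**2. The plan's own figure.** Section 8.2 states power above 80% for a relative risk of 2.0, at 2 MACE per 1,000 person-years with about 37,000 NB initiators. The abstract gives about 16,000 lorcaserin initiators. Mean follow-up and alpha are not stated; I assume two-sided 0.05. For a Wald test on the log rate ratio, SE = √(1/E_NB + 1/E_LOR).

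- At an assumed 1 year: E_LOR = 16,000 × 0.002 = 32; E_NB = 37,000 × 0.004 = 148; SE = 0.195; power = Φ(0.693/0.195 − 1.96) = 94.5%.
- At 0.5 year: 71%. Power reaches 80% at about 0.62 year.

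The stated figure is thus consistent with its inputs if mean follow-up is about 0.62 year or more. It makes no visible allowance for missed events.

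**3. Effect of capture.** Let c be the fraction of MI/stroke captured in a drug group and d the share of MACE that is cardiovascular death, assumed fully captured and equal in both groups. With no false positives:

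- MI/stroke: observed IRR = true IRR × c_NB / c_LOR.
- MACE: S = d + (1 − d)c; observed IRR = true IRR × S_NB / S_LOR.

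Every value of c, and d = 25%, is an assumption. At d = 25%, S = 0.625, 0.70, 0.775 and 0.85 for c = 50%, 60%, 70% and 80%.

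| c, NB | c, lorcaserin | True IRR | Observed, MI/stroke | Observed, MACE |
|---|---|---|---|---|
| 60% | 60% | 2.0 | 2.00 | 2.00 |
| 70% | 60% | 1.0 | 1.17 | 1.11 |
| 60% | 70% | 1.0 | 0.86 | 0.90 |
| 80% | 60% | 1.0 | 1.33 | 1.21 |
| 60% | 80% | 2.0 | 1.50 | 1.65 |
| 50% | 70% | 2.0 | 1.43 | 1.61 |

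**4. IRD and power with equal capture of 60%.** Take MACE rates of 4 v 2 per 1,000 (the plan's rate and relative risk).

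- With d = 25%, MI/stroke rates are 3.0 v 1.5. The MI/stroke IRD falls from 1.5 to 0.60 × 1.5 = 0.9 per 1,000 person-years, with 40% fewer events.
- The MACE IRD falls from 2.0 to 0.70 × 2.0 = 1.4, with 30% fewer events. If cardiovascular death were captured no better than MI/stroke, it would be 0.60 × 2.0 = 1.2.
- MACE power at 1 year falls from 94.5% to 84.5% (S = 0.70), or to 79% (S = 0.60).

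**The case against.** The plan is not silent on the problem. Adjudicated claims are linked for about 46% of EHR patients (7.1) and, at some point, about 64% of NB initiators (8.1), and section 6.2 reserves them for sensitivity analyses. Claims can show hospital care outside the contributing network. Section 9.4 names utilization as a surveillance proxy, and the covariate lists in 6.5.3 may not be exhaustive. Problem lists and medical history are in the extract (7.1), so an outside MI or stroke may be recorded at a later office visit. Deaths come from outside the EHR. The comparator shares the indication. The case-crossover analysis compares windows within a patient, so stable differences in capture between drug groups do not bias it.

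Most of this limits the size of the concern without removing it:

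- The claims are available, but no MI/stroke analysis using them is specified.
- The utilization sentence sits in the comparability paragraph, so its scope is unclear, and utilization is only a proxy for hospital capture.
- Section 6.5.2 does not say whether a later problem-list entry counts as an event or how it would be dated.
- Cause of death can fall back on EHR hospital or emergency records, so protection of that component is partial.
- A shared indication does not ensure a shared practice setting.
- The case-crossover analysis uses observed cases only and gives no NB-versus-lorcaserin IRR or IRD.

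A reader might infer that every outside MI or stroke is lost, or that the IRR is biased in a known direction. The documents support neither: later recording is possible, and there is no information on practice type by drug.

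**Conclusion.** The concern holds as a gap in design and analysis. As written, the plan counts person-time in which hospital-treated MI and stroke may be poorly visible, does not clearly adjust for that visibility, and does not estimate what is missed.

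Under-capture pulls the IRD toward zero and lowers the event count even when it is equal across drugs. The IRR is biased only if capture differs by drug, and then by the capture ratio, less for MACE to the extent that cardiovascular death is captured through the death link. In the illustrations a true null moves to between 0.86 and 1.33 for MI/stroke (0.90 to 1.21 for MACE), and a true 2.0 can fall to 1.43 (1.61 for MACE). These rest on assumed capture fractions, no false positives, and a 25% share of fully captured cardiovascular death. The actual size and direction cannot be derived from the documents.

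It might also be inferred that the power statement in section 8.2 is wrong. It is not shown to be: it agrees with its inputs at plausible follow-up, and the point is only that it carries no stated margin for missed events.

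**What to change.** 1. Prespecify a sensitivity analysis of MACE, MI and stroke (IRD and IRR) in claims-linked patients, with person-time limited to claims enrollment and MI/stroke identified from EHR or claims. Report EHR sensitivity for MI and stroke against claims, by drug.
2. State in 6.5.3 and 9.4 that the utilization and surveillance indicators also enter the main-objective propensity score. Where the extract identifies it, add a flag for whether the patient's contributor supplies inpatient or emergency encounters, report it by drug, and repeat the analysis in flagged patients.
3. Add under-capture of outcomes to section 10.1, with MI/stroke discussed separately from MACE.

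**Cost.** One or two further analyses in smaller, less precise sets. The claims link already exists; availability of the contributor flag is an assumption to confirm with the data supplier. Sensitivity by drug will be imprecise. If 64% of lorcaserin initiators were also linked (not stated), with one year of claims enrollment and 1.5 MI/stroke per 1,000, that gives 0.64 × 16,000 × 0.0015 = 15.4 events. An estimate of 60% would then carry about ±1.96 × √(0.6 × 0.4 / 15.4) = ±24 percentage points. The result should be read as a bound on plausible bias, not a correction factor.
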